6.5 Concomitant Medications

The use of drugs or vaccines explicitly prohibited in the exclusion criteria is prohibited during the entire study. If any explicitly prohibited drug or vaccine is clinically indicated during the study, the interruption of study treatment may be required. The investigator shall discuss with the sponsor's medical department. The decision whether the subject continues to participate in the study treatment or vaccination arrangements needs to be jointly decided by the investigator, the sponsor, and the subject. The investigator and/or the subject's attending physician shall make the final decision on supportive therapy or vaccination.

All drugs related to the treatment of AEs other than solvents within 28 days before the first dose of the study drug until 30 days after and 30-60 days after the end of the treatment should be documented in the CRF, including the name, dose, route of administration, frequency of administration, purpose, and start and end dates.

6.5.1 Permitted concomitant medications and/or treatment

During the treatment period, the investigator, per his/her judgment, may give the subject the best supportive treatment for the health of the subject. The clinical comorbidities and various AEs should be actively treated, especially immune-related adverse events (irAEs).

Subjects are allowed to receive bisphosphonate for the treatment of bone metastases. If systemic or local analgesia is not effective in controlling painful lesions of bone metastases, a small area of palliative radiotherapy irradiation (the area of the radiotherapy must be < 5% of the bone marrow region) is allowed.

Palliative treatment for lesions outside the lungs is allowed during the study (when the treatment of the subjects is needed to improve symptoms upon the onset of PD), including the treatments for pleural effusion, ascites, pericardial effusion, and radiotherapy for brain lesions. During such treatment, the study drugs should be interrupted until the end of the recovery period of palliative treatment.

6.5.2 Prohibited concomitant medications and/or treatment

Subjects are prohibited from the following therapies during the treatment period of this study:

- Systemic chemotherapy and biological therapy (anti-tumor drugs with immunomodulatory effects, including but not limited to interferon, interleukin-2, thymosin, and immune cell therapy)
- Immunotherapy not specified in this protocol;
- The use of other drugs not specified in the protocol, including Chinese patent medicines with clear anti-tumor indications (refer to Appendix 5)
- Radiotherapy (Note: As long as it is not a lung or target lesion, the sponsor may approve and allow radiotherapy to symptomatic isolated lesions or to the brain)
- Inoculation of live vaccines within 28 days before the first dose of the study medication and during the course of the study. Live vaccines include but are not limited to the following: rubeola, epidemic parotitis, rubella, chickenpox, yellow fever, rabies, BCG, and typhoid (oral) vaccines. Seasonal inactivated flu vaccines for injection are permitted but intranasal live attenuated flu vaccines (e.g., FluMist[®]) are not permitted
- Corticosteroids. Inhaled steroids are permitted as part of a fixed treatment for asthma or chronic obstructive pulmonary disease (COPD). Corticosteroids to treat potential irAE are permitted. After consultation with the sponsor, physiological doses of corticosteroids are permitted. Corticosteroids may be used prophylactically to prevent allergic reactions (such as intravenous contrast agent)

Based on the investigator's assessment, subjects who need to use any of the above therapies for clinical treatment should be excluded from the study. Subjects can receive other medications as deemed medically necessary by the investigator

It is important for the investigator to review each drug (prescription and over-the-counter) the subject receives before the start of the study and at each study visit.

- At each visit, the subject must be asked about any new medication received since the last visit

- In order to reduce the risk of drug interactions, all measures must be taken to limit the number of concomitant medications that are indeed necessary.
- During the administration period, drugs with hepatotoxicity should be avoided (i.e., drugs with hepatotoxicity warning in the package insert). The investigators are encouraged to review the potential hepatotoxicity of each drug at www.livertox.nih.gov.

6.5.3 Drugs that must be used with caution

1. Drugs that may have drug-drug interactions with apatinib

In vitro studies have shown that apatinib is primarily metabolized by the liver P450 enzyme CYP3A4. Apatinib has a strong inhibitory effect on CYP3A4 and CYP2C9, and has a moderate inhibitory effect on CYP2C19. CYP3A4 inducers (dexamethasone, carbamazepine, rifampicin and phenobarbital) and inhibitors (ketoconazole, itraconazole, erythromycin and clarithromycin), CYP3A4 substrates (simvastatin, cyclosporine and pimozide), and other drugs metabolized via CYP3A4 (such as benzodiazepines, dihydropyridine, calcium ion antagonist and HMG-COA reductase inhibitors) should be used with caution during the treatment. Omeprazole should be used with caution during the treatment (except when omeprazole must be used to treat serious adverse drug reactions).

The substrates of CYP2C9 and CYP2C19 should be used with caution, as shown in [Table 10](#).

Table 10. CYP2C9 and CYP2C19 substrates that should be used with caution

P450 Enzyme	Substrate
CYP2C9	Diclofenac, phenytoin, piroxicam, S-warfarin, and tolbutamide
CYP2C19	Diazepam, imipramine, lansoprazole, and S-mephenytoin

2. Drugs that prolong the QT interval of the heart

As tinib drugs may cause toxicities of prolonged QT interval in clinical applications, drugs that may prolong the QT interval should be used with caution during the study. These mainly include, but are not limited to, the following categories of drugs:

- Antibiotics: fluoroquinolones: sparfloxacin, gatifloxacin, levofloxacin, moxifloxacin, ofloxacin, ciprofloxacin; macrolides: erythromycin, clarithromycin, telithromycin, azithromycin, roxithromycin, and metronidazole
- Antiarrhythmics: quinidine, procainamide, disopyramide, flecainide, propafenone, amiodarone, dronedarone, sotalol, dofetilide, and ibutilide
- Drugs used to relieve angina pectoris: ranolazine, ivabradine

- Antipsychotics: risperidone, fluphenazine, droperidol, haloperidol, thioridazine, pimozide, olanzapine, and clozapine
 - Antifungal drugs: voriconazole, posaconazole
 - Antimalarial drugs: mefloquine, chloroquine
 - Antihistamines: terfenadine, astemizole, hydroxyzine
 - Gastrointestinal drugs: antiemetics: ondansetron, granisetron, dolasetron, droperidol (0.625 to 1.25 mg may be a safe dose), hydroxyzine; prokinetics: cisapride, domperidone, metoclopramide
 - Antidepressants: amitriptyline, imipramine, clomipramine, dosulepin, and doxepin
3. CYP3A4 substrates prohibited during the study (drugs with narrow safety windows and may cause serious adverse drug reactions when their metabolism is affected) include but are not limited to:
- Hypoglycemic agents: tolbutamide, chlorpropamide
 - Ergot derivatives: dihydroergotamine, ergometrine, ergotamine, methyl ergometrine (potential risk of ergot poisoning, including severe vasospasm leading to peripheral and cerebral ischemia)
 - Antipsychotic: pimozide (can potentially increase the risk of prolonged QT interval)
 - Antiarrhythmics: amiodarone (prohibited within 6 months prior to randomization), bepridil, flecainide, lidocaine, mexiletine, quinidine, and propafenone
 - Immunomodulators: cyclosporine, tacrolimus, sirolimus (may potentially increase the risk of nephrotoxicity and neurotoxicity)
 - Miscellaneous: quetiapine, risperidone, clozapine, tomoxetine hydrochloride
4. If warfarin is used for anticoagulation during the study, the dose should be reduced and closely monitored, and the study drug should be discontinued if necessary.
5. During the treatment period, anti-tumor drugs and adjuvant drugs related to anti-tumor treatments, such as anti-tumor traditional Chinese medicine (refer to Appendix 6) and immunological agents, shall be discontinued.

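### Protocol Section 6.5.3 lists nine drugs both as usable with caution and as prohibited, with no rule on which instruction governs; for eight of them nothing else settles use on study

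*Protocol*

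**What the plan says.** Section 6.5.3 is headed as a section on drugs needing caution. Within it:

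- **Item 1** states that "Apatinib has a strong inhibitory effect on CYP3A4 and CYP2C9" and asks for caution with, among others, "CYP3A4 substrates (simvastatin, cyclosporine and pimozide".
- **Table 10**, which belongs to item 1, gives the CYP2C9 substrates to be used cautiously as "Diclofenac, phenytoin, piroxicam, S-warfarin, and tolbutamide".
- **Item 2** asks for caution with drugs that may prolong the QT interval. Its antiarrhythmics include "quinidine, procainamide, disopyramide, flecainide, propafenone, amiodarone", and its antipsychotics include risperidone, pimozide and clozapine.
- **Item 3** changes the instruction. It lists "CYP3A4 substrates prohibited during the study" and describes them as "drugs with narrow safety windows and may cause serious adverse drug reactions when their metabolism is affected". One entry carries its own time limit: "amiodarone (prohibited within 6 months prior to randomization".

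Section 6.5.2, the section on prohibited treatments, names none of the nine drugs that appear on both sides. Its closing text includes "Subjects can receive other medications as deemed medically necessary by the investigator".

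**The concern.** Permission to use a drug carefully and a ban on that drug are different instructions, and here both apply to the same named products in one section. An investigator checking a drug against item 1, item 2 or Table 10 would conclude that it may be given with monitoring. One who reads on to item 3 would conclude that it may not. One who looks only in Section 6.5.2 would find no ban.

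What is at stake is patient safety. Item 3 rests its ban on narrow safety margins and on harm when metabolism is disturbed, and item 1 describes apatinib as the kind of inhibitor that would disturb it. Section 6.5.2 has investigators review every medication at each visit, and about 20 centers are planned, so the rule would be consulted often. It is also unclear whether giving one of these drugs would be a protocol deviation.

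The amiodarone entry raises a second point. A limit covering the 6 months before randomization acts as an eligibility rule, yet it is absent from Section 5.2 and from the synopsis exclusions. A site screening against those lists would miss it.

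**Working it through.** The plan states no figure to reproduce. The check compares the lists and then looks for other text that decides each overlapping drug.

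**Step 1: count the drugs named in item 3.** Hypoglycemics 2 + ergot derivatives 4 + antipsychotic 1 + antiarrhythmics 7 + immunomodulators 3 + miscellaneous 4 = 21.

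**Step 2: match them against the caution lists.**

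| Drug | Caution source | Class in item 3 |
|---|---|---|
| Cyclosporine | Item 1 | Immunomodulator |
| Pimozide | Item 1 and item 2 | Antipsychotic |
| Tolbutamide | Table 10 (CYP2C9) | Hypoglycemic |
| Quinidine | Item 2 | Antiarrhythmic |
| Flecainide | Item 2 | Antiarrhythmic |
| Propafenone | Item 2 | Antiarrhythmic |
| Amiodarone | Item 2 | Antiarrhythmic (6-month note) |
| Risperidone | Item 2 | Miscellaneous |
| Clozapine | Item 2 | Miscellaneous |

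Item 1 contributes 2, Table 10 contributes 1 and item 2 contributes 7, which makes 10 mentions. Pimozide is counted twice, so there are 10 − 1 = 9 drugs, and 9/21 = 43%. If the amiodarone note is read only as a limit before randomization, the overlap is 9 − 1 = 8.

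**Step 3: look for other text that decides use on study.**

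- Section 6.5 carries drugs barred by the exclusion criteria through the whole study. Exclusion 8 bars immunosuppressants, so cyclosporine is in effect settled. Item 5 of Section 6.5.3, which stops immunological agents, points the same way.
- Exclusion 24 (psychiatric history) and exclusion 21(4) (arrhythmia needing treatment, under a lead-in about heart disease that is not well controlled) describe patients at entry. They name no drug, so the Section 6.5 rule does not carry them forward as drug bans.
- No exclusion relates to tolbutamide.

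Unresolved on study: 9 − 1 (cyclosporine) = 8, or 8 − 1 = 7 on the narrow amiodarone reading.

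**Step 4: see how far entry criteria narrow the gap.** A related exclusion exists for cyclosporine (1), the four antiarrhythmics (4) and the three antipsychotics (3), and 1 + 4 + 3 = 8 of the 9. Exclusion 24 would reach most antipsychotic users. Exclusion 21(4) would reach antiarrhythmic users whose arrhythmia is not well controlled. What remains is drugs newly started on study, controlled arrhythmia, and tolbutamide.

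**The case against.** The best reply is that the two instructions can be obeyed together. Advice to be cautious gives no right to use a drug, and a site that follows item 3 breaks neither rule. The layout of Section 6.5.3 gives this some support. Warfarin appears under caution in Table 10 and then receives a stricter rule in item 4, and item 5 requires certain agents to be stopped even though it sits under the same heading. Item 3 could likewise be a later tightening for a high-risk subset. This is a sensible reading and probably the one intended, but the protocol does not state it. Both sides name the drugs individually, so neither is plainly the general rule that yields to the specific one.

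Other text helps in part:

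- Section 6.5 goes on to say that if an explicitly prohibited drug becomes clinically indicated, study treatment may have to be interrupted and the sponsor's medical department is consulted. That presupposes the drug is prohibited, which is the open question, and it follows a sentence about drugs barred by the exclusion criteria.
- Exclusion 27 lets the investigator exclude patients with serious illness, including mental illness, that needs concomitant treatment. It too concerns entry.
- Exclusion 21(4) could be read to exclude any clinically significant arrhythmia on treatment, controlled or not. That would shrink the gap at entry but would not touch drugs started later.
- The duties in Section 6.5.2 to review each drug and limit concomitant medication lower the risk, and its medically-necessary sentence concerns other medications and does not override item 3. None of this ranks the two lists.

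Two criticisms of size stand. Item 3 is an open-ended list, so 43% describes the overlap among named drugs and nothing clinical. The conflict also has no demonstrated effect on the efficacy analysis.

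**Conclusion.** The concern holds. Nine of the 21 drugs named in item 3 are also listed for cautious use in the same section (eight on the narrow amiodarone reading), and no precedence is stated. Eight (or seven) have no other text that settles their use on study. This count treats cyclosporine as settled by exclusion 8 and Section 6.5. That is a generous assumption, because Appendix 6 allows other immunosuppressive therapies under local guidelines for refractory Grade 3–4 hepatitis.

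The consequence is confined to patient safety and consistent conduct across sites. The number of subjects exposed cannot be derived from the documents. No effect on ORR, sample size or the per-protocol set is shown, and any effect on adverse event incidence would be indirect. The text is wrong as written and should be corrected, because it is an operative safety rule that can be read two ways.

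**What to change.** Either of two edits is enough:

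1. Add one sentence to Section 6.5.3 stating that item 3 prevails wherever a drug also appears in item 1, item 2 or Table 10.
2. Move the item 3 list to Section 6.5.2 and delete the nine drugs from item 1, item 2 and Table 10.

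The first is the smaller change; the second puts the ban where a site would look for it. Item 3's stated reason favors prohibition over caution.

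If the 6-month amiodarone restriction is intended, add it to the exclusion criteria in Section 5.2 and the synopsis, and say in Section 6.5 whether amiodarone is also barred during treatment.

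The cost is protocol wording only, with no change to the design, sample size or analysis.

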6.6 Medication During Pregnancy, Childbearing Age, and Lactation

The following lists the special restrictions on concomitant medications during the study period. Medication during pregnancy, childbearing age, and lactation

6.6.1 Pregnancy

SHR-1210 is an IgG4 that can cross the placental barrier. It has been suspected/confirmed to have teratogenicity/fetal toxicity. Pregnant women must not be enrolled in the study.

6.6.2 Childbearing potential

Women of childbearing potential must have a negative serum pregnancy test within 3 days prior to the first dose of the study drug.

Female subjects of childbearing age and male subjects with partners of childbearing age should be sterilized or agree to take highly effective contraceptive measures during the study period and 24 days after the last study dose.

After consulting with the subject, the investigator or designated personnel will select appropriate contraceptive methods for the subject and his/her partner from the following contraceptive methods, and confirm the subject's awareness of correct and consistent use the contraceptive method. At time points shown in the Schedule of Activities, the investigator shall notify the subject of the persistent and correct use of contraception. The subject should be aware that the investigator must be notified immediately once the selected method of contraception is stopped, or when the subject or the partner is suspected or confirmed of pregnancy.

An effective contraception method refers to a method with an annual failure rate of < 1% when correctly used independently or with other methods, including:

1. Commonly used hormonal contraceptive methods associated with the suppression of ovulation (e.g., oral, inserted, injectable, implants, subcutaneous) should meet the requirement that the female subject or partner of male subject has been using this method for a period of time with proven effectiveness, and plans to continue using it correctly throughout the study.
2. Correctly inserted intrauterine devices.
3. Male/female condom combined with topical spermicides (i.e., foams, gels, films, creams, or suppositories).
4. Male sterilization by vasectomy.
5. Bilateral tubal ligation/bilateral salpingectomy or bilateral tubal occlusion (the occlusion should be proven effective by relevant instruments).

Menopause refers to 12 months of amenorrhea in women ≥ 45 years old without biological or physiological reasons:

1. Women \leq 55 years old must have a serum follicle-stimulating hormone (FSH) test, i.e., FSH $>$ 40 mIU/mL to prove menopause
2. Women who use hormone replacement therapy (HRT) may artificially suppress FSH levels and require a certain washout period to obtain a normal physiological level of FSH. The investigator is recommended to determine the washout period based on the level of FSH. Any serum FSH $>$ 40 mIU/mL during the washout period is considered menopause. Recommended duration of the washout period:
 - \geq 1 week for vaginal hormone products (rings, ointments, and gels)
 - \geq 4 weeks for transdermal products
 - \geq 8 weeks for oral products

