8. Hematology includes: red blood cell count (RBC), hemoglobin (HGB), hematocrit value (HCT), white blood cell count (WBC), platelet (PLT), and white blood cell differential [lymphocyte count (LYM), absolute neutrophil count (ANC), monocyte count (MONO), eosinophil count (EOS), and basophil count (BASO)]. Clinical chemistry includes: liver function [serum total bilirubin (TBIL), alanine aminotransferase (ALT), aspartate transferase (AST), gamma-glutamyltransferase (γ -GT), alkaline phosphatase (ALP), albumin (ALB), total protein (TP), and lactic dehydrogenase (LDH)]; renal function [blood urea nitrogen (BUN) and creatinine (Cr)]; blood electrolytes (Na, K, Cl, Mg, Ca, and P); lipase, amylase, and fasting blood glucose (FBG). Urinalysis includes: pH, urine albumin (UALB), urine protein (UPRO), urine red blood cell (URBC), and urine glucose (UGLU). The subject may be enrolled only if urinalysis shows negative urine protein at screening. Routine stool test: occult blood; re-examination is needed for fecal occult blood+; if fecal occult blood is confirmed, then a gastroenterological endoscopy will be performed. Hematology, clinical chemistry, urinalysis, and routine stool will be performed during the screening period (within 7 days before the first dose of the study drug), before each SHR-1210 administration, at the end of the treatment, and at safety follow-ups. Tests will be performed at each study center.
9. Coagulation function tests include: thrombin time (TT), prothrombin time (PT), activated partial thromboplastin time (APTT), and international normalized ratio (INR). Tests will be performed within 7 days prior to the first dose, before the administration of SHR-1210 on day 1 of each cycle, at the end of the treatment, and at safety follow-ups. Tests will be performed at each study center.
10. Women of childbearing potential will undergo a serum pregnancy test within 3 days prior to the first dose and at the end of the treatment. Tests will be performed at each study center.
11. Thyroid function tests include: thiiodothonine (T3), thyroxine (T4), free thiiodothonine (FT3), free thyroxine (FT4), and thyroid stimulating hormone (TSH). Tests will be performed during the screening period, before the administration of SHR-1210 on day 1 of each cycle, at the end of the treatment, and at safety follow-ups; the results from the screening period may be used for the thyroid function tests at the C1D1 visit. Tests will be performed at each study center.

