5 STUDY POPULATION

5.1 Inclusion Criteria

Patients must meet all of the following inclusion criteria to be eligible for this study.

1. All patients must sign an ICF prior to starting any study-related procedures
2. Aged ≥ 18 and ≤ 70 years
3. Histologically or cytologically confirmed small cell lung cancer
4. Staged ED-SCLC according to VALG staging
5. Have previously received first-line platinum-based treatment for ED-SCLC and have shown objective imaging progression. Including:
 - Sensitive recurrence: progression in ≥ 90 days from the last chemotherapy
 - Drug-resistant recurrence: progression during chemotherapy or within 90 days from the last chemotherapy
6. Able to provide tumor tissue samples for diagnosis, either archived samples within 12 months prior to the first dose of study drug or freshly obtained. The specimens shall meet the requirements of formalin-fixed and paraffin-embedded (FFPE) tumor tissue blocks allowing the cutting of at least 5-10 slices with a thickness of 4-6 μm for staining and testing. Cell smears from fine needle aspiration or centrifuged pleural fluid, bone lesions without soft tissue components or decalcified bone tumor specimens, and drill biopsy tissues are not acceptable, as they are insufficient for biomarker detection
7. ECOG PS of 0-1
8. Life expectancy of ≥ 8 weeks
9. With at least one target lesion without previous radiotherapy (RECIST v1.1) shown by CT or MRI scan ≤ 28 days prior to the first dose of study drug
10. Males and females of reproductive potential must take contraceptive measures from the first dose of study drug to within 24 weeks after the last dose of study drug (see 6.6.2 of the protocol for recommended contraceptive methods)
11. Had no transfusion of blood or blood products within 14 days prior to the first dose, not corrected with G-CSF or other hematopoietic colony-stimulating factors. Before the first dose of study drug, laboratory test values must meet the following conditions:
 - (1) Hematology: $\text{WBC} \geq 3.0 \times 10^9/\text{L}$; $\text{ANC} \geq 1.5 \times 10^9/\text{L}$; $\text{PLT} \geq 100 \times 10^9/\text{L}$; $\text{HGB} \geq 9.0 \text{ g/dL}$

- (2) Liver function: AST $\leq 2.5 \times$ ULN, ALT $\leq 2.5 \times$ ULN for patients without liver metastasis; ALT and AST $< 5 \times$ ULN for patients with liver metastasis; TBIL $\leq 1.5 \times$ ULN (TBIL < 3.0 mg/dL in patients with Gilbert syndrome); and ALB ≥ 3 g/dL

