7.2.4 Safety follow-up

Safety follow-ups will be performed 90 ± 7 days after the last dose (refer to [Table 14](#)).

Table 14. Procedures of the safety follow-ups

Period	Safety Follow-Up	Note
Day	28 Days (± 7 Days)	
Vital Signs	X	Vital signs include body temperature, pulse, respiratory rate, and blood pressure. See Section 8.2.4 of the protocol for detailed requirements
Body Weight	X	
Physical Examination	X	See Section 8.2.2 of the protocol
ECOG PS	X	
Laboratory tests		
12-Lead ECG	X	Refer to Section 8.2.3 of the protocol for details
Hematology/Clinical Chemistry/Urinalysis/Routine Stool	X	See Section 8.2.1 of the protocol
Coagulation Function	X	
Thyroid Function	X	
Immunogenicity (ADA, Nab)	X	

Period	Safety Follow-Up	Note
Day	28 Days (\pm 7 Days)	
AE Assessment	X	All AEs from the time of signing the ICF to the end of safety follow-up or the start of new anti-tumor therapy (whichever occurs first) and all SAEs from signing of ICF to the end of safety follow-up will be recorded in the CRF
Concomitant Medications	X	Drugs related to the treatment of AEs other than solvents within 28 days before the first dose of the study drug until 30 days after and 30 to 60 days after the end of the treatment should be documented
End of treatment visit		
Survival Status	X	
Subsequent Anti-Tumor Treatment	X	
Response Evaluation		
Imaging Assessment	X	If the treatment is discontinued for reasons other than radiologically confirmed PD, imaging evaluations shall be performed as much as possible per the scheduled time points until any of the following events occurs: start of new anti-tumor therapy, PD, withdrawal of ICF, or death.

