8.2.6 Pregnancy test

Women of childbearing potential undergo a serum human chorionic gonadotropin (hCG) pregnancy test within 3 days before the first dose of the study drug. Subjects with a positive result are not eligible or must discontinue participation in the study. Retests will be performed when pregnancy is suspected during the study period.

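### Protocol 6.6.2 ends contraception 24 days after the last dose, where inclusion criterion 10 requires 24 weeks; 6.6.2 should say 24 weeks

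*Protocol*

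**What the plan says.** Three places in the current protocol state how long contraception must continue.

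- **Section 5.1, inclusion criterion 10**: men and women able to have children "must take contraceptive measures from the first dose of study drug to within 24 weeks after the last dose of study drug".
- **Synopsis, inclusion criterion 10**: the same requirement, also 24 weeks.
- **Section 6.6.2**: women of childbearing age, and men whose partners are of childbearing age, are to be sterilized or else "agree to take highly effective contraceptive measures during the study period and 24 days after the last study dose".

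Both copies of criterion 10 point to 6.6.2 ("see 6.6.2 of the protocol for recommended contraceptive methods"). Section 6.6.2 also carries the counselling duty. It has the investigator choose a method with the subject and confirm that it is understood, and at scheduled time points "the investigator shall notify the subject of the persistent and correct use of contraception".

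On risk, section 6.6.1 notes that SHR-1210 can cross the placenta and adds: "It has been suspected/confirmed to have teratogenicity/fetal toxicity". The SAP does not mention contraception.

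**The concern.** One participant-protection rule has two durations, with the same numeral and different units. The shorter one sits in the section an investigator would open when advising a subject. Criterion 10 is checked at entry, whereas 6.6.2 is used during treatment and when treatment stops, which is when the post-dose duration matters.

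A site working from 6.6.2 could tell a subject or partner to stop contraception months before criterion 10 allows. There is little to catch this later. Note 10 to the Schedule of Activities says women of childbearing potential "will undergo a serum pregnancy test within 3 days prior to the first dose and at the end of the treatment". Table 14 lists no pregnancy test at the safety follow-up, and section 8.2.6 provides only that "Retests will be performed when pregnancy is suspected during the study period". After the last dose, protection rests mainly on what the subject was told.

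**Working it through.** **Inputs**

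| Item | Value | Source |
|---|---|---|
| Post-dose contraception, criterion 10 | 24 weeks | Synopsis; Protocol 5.1 |
| Post-dose contraception, 6.6.2 | 24 days | Protocol 6.6.2 |
| Safety follow-up visit | 90 ± 7 days after last dose | Protocol 7.2.4 |
| Survival follow-up | every 8 weeks after last dose | Protocol 7.2.5 |

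**Stated figures in one unit**

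- Criterion 10: 24 × 7 = 168 days.
- Ratio: 168 / 24 = 7.
- Difference: 168 − 24 = 144 days.

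**Shortfall under each reading of *study period***

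Section 6.6.2 requires contraception during the study period as well as for 24 days after the last dose. The obligation therefore ends at the later of the two, and the protocol does not define the term for an individual subject.

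- *Treatment period only*: ends at day 24. Shortfall 168 − 24 = **144 days**.
- *Up to the safety follow-up* ("Safety follow-ups will be performed 90 ± 7 days after the last dose"): the visit falls on day 83 to day 97.
  - Day 83: 168 − 83 = **85 days**
  - Day 90: 168 − 90 = **78 days**
  - Day 97: 168 − 97 = **71 days**
- *Including survival follow-up*: three contacts at 8-week intervals reach 3 × 8 = 24 weeks, so the shortfall may be **zero**.

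**Which reading fits the sentence**

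If the study period already ran to day 83 or beyond, the 24-day clause would add nothing, because day 24 would lie inside it. The clause has a function only if the study period ends at about the last dose. That favors the 144-day reading but does not prove it.

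**Which figure is likely to be right**

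- The 24-week figure is an eligibility requirement. It appears twice, though the synopsis entry is a copy of section 5.1 and not independent support.
- The numeral is the same in all places and only the unit differs.
- Section 2.3.2 reports serum levels of 4000 to 9000 ng/mL on Day 15 after a single dose of 3 mg/kg or a fixed 200 mg, against at least 2000 ng/mL needed for receptor saturation. Day 24 is only nine days later, and trial subjects receive repeated doses. With no half-life given, this does not derive 24 weeks, but it lends no support to stopping at day 24.
- Section 9.1.1 collects adverse events to 90 days after the last dose, so a 24-day limit would end contraception well inside that window.

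**The case against.** The strongest reply is that the two rules do not strictly conflict. A subject who follows the longer one satisfies both, criterion 10 is an eligibility condition that section 5.3 says admits no exceptions, and it cites 6.6.2 for methods and not for duration. The wording also differs: criterion 10 covers people of reproductive potential and asks for contraceptive measures, while 6.6.2 covers females of childbearing age and males with partners of childbearing age and asks for highly effective measures. Harm requires a site to follow 6.6.2 and overlook the criterion. This stands as a limit on the likelihood of harm. It does not explain why the counselling section should give a period one seventh as long to what are largely the same people.

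A second reply uses the synopsis row on the study period, which describes the whole trial from Q1 2018 to Q1 2020, together with section 6.1.3, which places completion 180 days after the last subject's first dose. On that trial-level reading, a subject who stops early might be bound for longer than 24 weeks, and the proposed wording would shorten that obligation. The reading is strained for a duty placed on an individual, because it would tie each subject's contraception to other people's enrollment and leave the 24-day clause doing little. It does confirm that 144 days is a maximum.

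Two smaller points are fair. The direction of the correction is an inference, since neither figure is derived in the documents. And the pregnancy-test row in Table 13 carries no mark at end of treatment, although Table 1 and its note 10 schedule one.

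**Conclusion.** The inconsistency is real and lies in current text. The stated limits are 24 and 168 days after the last dose, a factor of 7. The practical shortfall under 6.6.2 is 0 to 144 days depending on how *study period* is read, with 144 days the most natural reading.

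Confidence is high that the texts disagree. That 24 weeks is the intended figure is well supported but rests on internal consistency and on its being the more protective stated limit, not on a stated derivation. The consent form was not available, so it is unknown which figure subjects are given. The number of subjects affected cannot be worked out from the documents. Because criterion 10 remains in force, this is a defect that should be corrected and not evidence that subjects were misadvised. It has no bearing on sample size, endpoints or analysis.

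**What to change.** In 6.6.2, change the unit from days to weeks, and replace the undefined study-period wording with criterion 10's own limits, so that the obligation runs from the first dose of study drug until 24 weeks after the last. The sponsor may confirm the 24 weeks against the two Investigator's Brochures. Check that the consent form and any site counselling text give the same period.

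The cost is a one-line correction and a document check. Section 14.3 requires ethics committee approval of protocol and consent form revisions, which is routine for a change of this kind. Nothing in the statistical design or analysis changes.
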